### 4.4.2 Labeling of Investigational Product

Investigational product will be labeled according to the requirements of local law and legislation.

## 4.4.3 Packaging of Investigational Product

The sponsor will be responsible for ensuring that the IP is manufactured in accordance with applicable current Good Manufacturing Practice regulations and requirements.

## 4.4.4 Storage of Investigational product

C19-IG 20% must be stored in a secure area accessible to study personnel authorized by the investigator, such as the study staff responsible for the preparation and dispensing of IP.

C19-IG 20% must be stored at temperatures of 2°C to 8°C (36°F to 46°F) and protected from light. Do not freeze or partially freeze. Investigators, or designees, are responsible for maintaining storage temperature records and for immediately reporting deviations in temperature to the study monitor.

Details for the storage are located in the Pharmacy Manual provided to each site.

All partially used vials should be discarded as no preservative is present. Do not use after expiration date.

The pharmacist must keep IP accountability by means of an accountability log.

# 4.5 Expected Duration of Subject Participation in the Study

Subjects will receive one blinded C19-IG 20%/Placebo dose via SC route on Day 1; for all subjects monitoring and surveillance will be continued throughout the subject's participation in the study. The total estimated maximum duration of a subject's participation in terms of actual Healthcare Provider Visits will be up to 30 days. Additionally, a Phone Check will occur at Day 60 for complete follow-up. Thus, subject participation (from Screening Visit to the Final Phone Check) will be approximately 60 days.

	Number BIG-CL-F	BIG-CL-PRT-000028	Version 5.0	5.0	Status	Effective	Effective Date	te 13-Oct-2021	
75	GC2010 - A Multicent	ter, Randomized, Dou	ble-blind, Parallel Gro	up Study to Evalua	ate t	he Safety and Efficacy of	~~ ~	56 of 106	
	Anti-COVID-19 Immi	19 Immine Globiilin (Human) 20% (C19-IG 20%) versus Pla	9-1G 20%) ve	rsis Placeho	in Asymptoma	tic Ambulatory	raye	001 10 00	_

GRIFOLS

# 4.6 Discontinuation Criteria for Individual Subjects and Study

## 4.6.1 Discontinuation Criteria for Individual Subjects

See Section 5.3 Subject Withdrawal Criteria

## 4.6.2 Premature Termination of Study/Closure of Center

The sponsor, Institutional Review Board/Ethics Committee (IRB/EC), and/or regulatory authorities have the right to close this study or a study center, and the investigator/sponsor has the right to close a center, at any time, although this should occur only after consultation between involved parties. The IRB/EC must be informed. Should the study/center be closed prematurely, all study materials (except documentation that has to remain stored at the site) must be returned to the sponsor. The investigator will retain all other documents until notification given by the sponsor for destruction.

The reasons a study center may be closed include, but are not limited to, the following:

- Lack of enrollment
- Non-compliance with the requirements of the study protocol
- Non-compliance with ICH GCP

# 4.7 Accountability Procedures for Investigational Product

Investigational product is to be used only for the study in accordance with the directions given in this protocol. The investigator, or designee such as the study pharmacist or specifically designated unblinded nurse, is responsible for handling of the IP in accordance with directions given in the protocol.

The investigator is responsible for maintaining accurate records of the IP for his/her site. Investigational product inventory/dispensing documentation verifying the receipt, dispensing, destruction, or return must be maintained and kept current by the investigator, or designee. The inventory must be made available for inspection by the monitor. Investigational product supplies must be accounted for by the monitor and inventory/dispensing logs must be verified by the monitor prior to IP return or destruction. Written documentation of any used and unused inventory is required. At the end of the study, a copy of the inventory/dispensing log(s) will be retrieved by the monitor and returned to Grifols.

#### 4.8 Maintenance of Treatment Randomization Codes

Randomization codes will be generated and access to the actual randomization schedules or codes must be strictly controlled during the course of the study. This study is double-blind so there is blinding of treatment assignment.

	Number	Number BIG-CL-PRT-000028	Version	5.0	Status	Effective	Effective Date	13-Oct-2021
	GC2010 - A	Multicenter, Randomized, Double-blind	, Parallel Gro	oup Study to l	Evaluate the Sa	fety and Efficacy of		2013
rial Group Anti-COVID-19 Imm	Anti-COVID-	19 Immune Globulin (Human) 20% (C1	9-IG 20%) ve	ersus Placeb	o in Asymptoma	itic Ambulatory	rage	5/ of 106

#### 4.9 Data to Be Recorded

All information contained in the medical history and complementary exploration reports including laboratory test will be considered as clinical trial source data.

Any data recorded in the Case Report Form should have written or electronic record in the subject's medical records. These written or electronic records will be considered source data and should be dated and signed by the investigator or by the qualified delegated person (eg, results of vital signs testing, or the IP administration procedure).

For every subject enrolled, the investigator will write into his/her medical history that he/she has been enrolled in a clinical trial, specifying its title, study number, and sponsor (Grifols Therapeutics LLC), as well as the date of informed consent form (ICF) provision.

The investigator is responsible for maintaining complete and adequate case histories in source records of each subject. All study-specific data necessary to be recorded that cannot be found in subjects' past medical records (such as medical history, past medications, etc) should be recorded by the investigator or their designee in subjects' medical files, dating and signing all new entries.

Source data must be preserved for the maximum period of time as required per local and international regulations and made available by the investigator in the cases described above.

#### SELECTION AND WITHDRAWAL OF SUBJECTS 5

#### 5.1 Inclusion Criteria

A subject must meet all the following inclusion criteria to be eligible for participation in this study:

- 1. Ambulatory male or female outpatients ≥ 18 years of age who have laboratory-confirmed SARS-CoV-2 infection as determined by qualitative PCR (RT-PCR), or other commercial or public health assay approved by regulatory authorities as a diagnostic test for COVID-19 (inclusive of SARS-CoV-2 antigen testing or other approved rapid testing platforms) in any specimen  $\leq 5$  days prior to randomized treatment. (Note:  $\leq 5$  days is the post-sampling timeframe from date specimen obtained to administration of blinded study drug).
  - Note: Every effort should be made to reduce this time interval to the minimum as nearly immediate treatment is key for successful intervention. For instance, if SARS-CoV-2 antigen testing is used for diagnostic purposes the subject may be able to receive the study drug the same day testing is performed.
- 2. Asymptomatic with no constitutional COVID-19 illness (evident symptoms), specifically no fever, cough, shortness of breath, fatigue, anorexia, vomiting/diarrhea, headache that is unrelated to pre-existing conditions (eg, migraine), sore throat that is unrelated to other pre-existing medical conditions (eg., allergies, gastroesophageal reflux disease), myalgias,

₽

- olfactory disorders unrelated with previous medical condition, or evidence of pneumonia at Screening.
- Pulse oximetry SpO2 (oxygen saturation) on room air > 94% (ie, 95% to 100%) at Screening.
- 4. National Early Warning Score (NEWS) ≤ 2 points (Appendix 2) at Screening.
- 5. Subject provides informed consent (ICF) prior to initiation of any study procedures.

#### 5.2 Exclusion Criteria

A subject meeting any of the following exclusion criteria is NOT eligible for participation in the study.

- 1. Subjects who are admitted to hospital or for whom hospital admission is being planned at the time of Screening.
- Subjects requiring any form of oxygen supplementation at Screening.
- 3. Concurrent or planned treatment with other agents with actual or possible direct antiviral activity against SARS-CoV-2 including remdesivir.
- 4. Prior, concurrent or planned treatment with mAbs against SARS-CoV-2
- 5. Have participated in a previous SARS-CoV-2 vaccine study OR outside of a study have received any SARS-CoV-2 vaccine of any kind.
- 6. Have a history of convalescent COVID-19 plasma treatment at Screening.
- 7. Fever (temperature ≥38.0° C [≥100.4° F]) measured orally, requirement for antipyretics to reduce temperature (administered for fever), and/or respiratory symptoms (cough, dyspnea) at Screening.
- 8. Clinical evidence of any significant acute or chronic disease that, in the opinion of the investigator, may place the subject at undue medical risk for study treatment.
- The subject has had a known (documented) history of serious anaphylactic reaction to blood, any blood-derived plasma product or commercial immunoglobulin, or has known selective IgA deficiency with anti-IgA antibodies.
- 10. Decompensated congestive heart failure or renal failure with fluid overload. This includes currently uncontrolled congestive heart failure New York Heart Association Class III or IV stage heart failure.
- 11. Subjects for whom there is limitation of therapeutic effort such as "Do not resuscitate" status.
- 12. Currently participating in another interventional clinical trial with investigational medical product or device.
- Subjects with known (documented) thrombotic complications to polyclonal IVIG therapy in the past.
- 14. Subject has medical condition (other than COVID-19) that is projected to limit lifespan to ≤ 1 year.

	Number	BIG-CL-PRT-000028	Version	2.0	Status	Effective	Effective Date	13-Oct-2021
CIVILOES	GC2010 - A	Multicenter, Randomized, Double-blind	, Parallel Gro	up Study to	Evaluate the Sa	ifety and Efficacy of	0000	901 J~ 03
Bioscience Industrial Group	Anti-COVID-1	9 Immune Globulin (Human) 20	)% (C19-IG 20%) ve	rsus Placeb	o in Asymptoma	itic Ambulatory	Tage	001 10 60

- 15. Subject has history of drug or alcohol abuse within the past 12 months.
- 16. Subject is unwilling to commit to follow-up visits.
- 17. Women who are pregnant or breastfeeding, or if of childbearing potential, unwilling to practice a highly effective method of contraception (oral, injectable, or implanted hormonal methods of contraception, placement of an intrauterine device or intrauterine system, condom, or occlusive cap with spermicidal foam/gel/cream/suppository, male sterilization, or true abstinence\*) throughout the study.
  - \* True abstinence: When this is in line with the preferred and usual lifestyle of the subject. (Periodic abstinence [eg, calendar, ovulation, symptothermal, post-ovulation methods], declaration of abstinence for the duration of a trial, and withdrawal are not acceptable methods of contraception).

Note: Women who are > 55 years and with absence of menses in the last 12 months are considered Not to be of childbearing potential. Female subjects of child-bearing potential must have a negative test for pregnancy blood or urine human chorionic gonadotropin (HCG)-based assay at Screening/Baseline Visit.

# 5.3 Subject Withdrawal Criteria

Subjects have the right to withdraw from the study at any time for any reason, either before or after the infusion of the IP. The investigator can withdraw a subject from the clinical trial at any time.

The investigator will document the reason(s) for withdrawal of each subject in source documents and study record. All data gathered on the subject prior to termination will be made available to the sponsor.

#### 5.3.1 Screen Failures

Screening evaluations will be used to determine the eligibility of each subject for enrollment. Subjects who fail to meet eligibility criteria during screening evaluations will be considered screen failures and will not participate in the study. Outcomes of screening evaluations will be documented in subject's source documents (e.g. medical history) - including compliance with each individual inclusion/exclusion criterion- and in study records as well.

#### 5.3.2 Removal of Subjects

Subjects may withdraw or be withdrawn from the study for the following reasons:

- 1. At their own request or at the request of their legally acceptable representative.
- 2. If, in the investigator's opinion, continuation in the study would be detrimental to the subject's well-being.
- 3. At the specific request of the sponsor.

Also, subjects may be withdrawn for the following reasons:

	Number BIG-CL-PR	BIG-CL-PRT-000028	Version	5.0	Status	Effective	Effective Date	13-Oct-2021
2	GC2010 - A Multicente	Multicenter, Randomized, Double-blind	, Parallel Gro	up Study to E	valuate the Sa	ety and Efficacy of		0073
Group	Anti-COVID-19 Imm	une Globulin (Human) 2	0% (C19-IG 20%) ve	ersus Placebo	in Asymptoma	tic Ambulatory	rage	90 T TUB

- 1. The subject is not able to adhere to the main protocol requirements (major protocol violations).
- 2. The occurrence of an adverse event (AE) which in the investigator's opinion requires the withdrawal of the subject from the clinical trial.
- 3. The subject is lost to follow-up.
- 4. Subject's death.
- 5. Any event which in the opinion of the investigator impedes the subject's participation in the study.

In all cases, the reason for withdrawal must be recorded in the study record and in the subject's records.

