#### 4.4 Study Treatments

#### 4.4.1 Treatments to Be Administered

Anti-COVID-19 Immune Globulin (Human) 20% (C19-IG 20%) is a sterile liquid formulation of immunoglobulin that has been purified from donors with high-titer anti-SARS-CoV-2 antibodies. Specifically, to qualify for product manufacture the convalescent plasma units must have anti-SARS-Cov-2 antibody titer ≥7.0 using the Architect-Abbott method or  $\geq 10.0$  using the Vitros-Ortho method.

The human plasma is purified via a multi-step process. C19-IG 20% is manufactured using the same process as for IGIV-C 10% (Immune Globulin Intravenous [Human], 10% Caprylate/Chromatography Purified [IGIV-C]) and is further concentrated by ultrafiltration to a higher IgG concentration (20%). Concentration employs the same procedures as Grifols commercially available SC product, XEMBIFY® (IGSC 20%) which is approved in the US and Canada for PI.

C19-IG 20% is a sterile liquid formulation of 20% human immune globulin formulated in 0.16 to 0.26 M glycine and 10 to 40 µg/mL Polysorbate 80 (PS80) at pH 4.1 to 4.8. It will be supplied in 5 mL and 10 mL vial sizes containing a 20% solution of immunoglobulin (ie, a concentration of 20 g/100 mL [200 mg/mL]).

C19-IG 20% must be inspected visually before being administered. The solution must not be used if the solution is cloudy or turbid. Solution that has been frozen should not be used. The investigator, or designee, is responsible for immediately reporting any issues noted with C19-IG 20% to the study monitor.

For placebo, sterile 0.9% sodium chloride injection United States Pharmacopeia (0.9% NaCl, USP) or equivalent will be used as a placebo to maintain the blind.

Detailed IP administration instructions are provided in Section 6.

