#### 5.3.4 Follow-up of Subjects Withdrawn from Study

For subjects administered any amount of blinded IP who discontinue the clinical trial details for follow-up are delineated below.

For subjects who withdraw from the clinical trial (excluding screen failures), study procedures and assessments scheduled for the Day 14 Visit will be performed at the time of withdrawal, during an unscheduled visit at the time of withdrawal. In addition, to assure major clinical outcomes are adequately captured as a measure of overall safety, these subjects will be asked to attend their chronological Day 29 Healthcare Provider Visit (ie, 28 days after Day 1 baseline), unless the unscheduled visit is within 4 days of their chronological Day 29 visit, and provided that they or their legally acceptable representative have not withdrawn consent. At the chronological Day 29 Healthcare Provider Visit, all assessments will be performed. These subjects will also have a Phone Checks on Day 60 as follow-up after the Day 29 Final Healthcare Provider Visit.

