### 4.2 Analysis Populations

The following four analysis populations will be defined for this study:

The intent-to-treat (ITT) population is defined as all subjects who are randomized.

The modified intent-to-treat (mITT) population is defined as the subset of subjects included in the ITT who are also dosed. The mITT population will be used for all efficacy analyses. As sensitivity analysis, the primary efficacy analysis will also be carried out using the ITT population if different from the mITT population.

The Per-Protocol (PP) population is defined as the subset of subjects included in the mITT population who do not present major protocol violations which might have an impact on the primary efficacy endpoint(s), and complete at least 80% of the IP. The primary efficacy analyses will be carried out using the PP population if different from the mITT population.

The Safety (SAF) population is defined as subjects who receive at least any amount of blinded C19-IG 20%/Placebo. All safety analyses will be carried out using the SAF population based on the treatment actually received rather than randomized treatment.

The validity of a subject for inclusion in each of these populations (ITT, mITT, Safety, and PP) will be assessed before unblinding the database and documented in a blinded review report.

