#### 4.6 Data Derivations and Transformations

The following derivations will be used in this study:

Study Day:

- Date of assessment date of study drug administration + 1 for assessments done on or after date of study drug administration
- Date of assessment date of study drug administration for assessments done before date of study drug administration

Baseline Observation: the last non-missing value prior to study drug administration.

Duration:

• Duration in days = end date - start date + 1

• Duration in minutes = end time in minutes – start time in minutes

Origin or Start Date for Time to Event Endpoints:

- Time to negative SARS-CoV-2 by PCR: date of study drug administration
- Time to Clinical Progression: date of study drug administration
- Time to COVID-19 symptoms through Day 14: date of study drug administration

Event Date for Time to negative SARS-CoV-2 by PCR:

• The date of the first negative result from the SARS-CoV-2 assessment by PCR will be used as the event date for deriving time to negative SARS-CoV-2.

Event Date for Time to Clinical Progression

• The event date will be the date of death, the start date of invasive mechanical ventilation, or the date of ICU admission/requiring ICU level of care, whichever occurs first.

Event Date for Time to COVID-19 symptoms through Day 14

• The event date will be the first time point when any element of the case definition for primary efficacy variable is fulfilled through Day 14

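### Subjects removed before Day 14 for violations or at the sponsor's request stay in mITT, but required ascertainment of their primary endpoint stops; follow-up of undosed subjects is unclear

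*Protocol*

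**What the plan says.** Protocol 4.5 sets the dosing: "Subjects will receive one blinded C19-IG 20%/Placebo dose via SC route on Day 1". Protocol 5.3.2 then lists grounds for withdrawal from the study. One is the sponsor's specific request, with no criterion attached. Another is "The subject is not able to adhere to the main protocol requirements (major protocol violations". Protocol 5.3 also lets the investigator withdraw a subject at any time, and 5.3.3 bars replacement after randomisation.

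Protocol 5.3.4 describes follow-up after withdrawal. It opens: "For subjects administered any amount of blinded IP who discontinue the clinical trial details for follow-up are delineated below". The next sentence has a broader scope: "For subjects who withdraw from the clinical trial (excluding screen failures), study procedures and assessments scheduled for the Day 14 Visit". On timing, that same sentence brings those procedures forward, since they "will be performed at the time of withdrawal, during an unscheduled visit at the time of withdrawal". Subjects are then asked to a chronological Day 29 visit unless consent has been withdrawn (or the withdrawal visit falls within 4 days of it), followed by a Day 60 phone check. The section gives overall safety as the reason for this retained follow-up.

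The primary endpoint is remaining free of symptomatic COVID-19 through Day 14. The primary set, mITT, is everyone randomised and dosed. PP excludes major violators. ITT is everyone randomised, and SAP 4.2 says: "As sensitivity analysis, the primary efficacy analysis will also be carried out using the ITT population if different from the mITT population". SAP 4.6 counts Study Day from dosing, adding "1 for assessments done on or after date of study drug administration", while SAP 4.3 summarises data by nominal visit.

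**The concern.** With a single dose already given, withdrawal leaves no study treatment to stop; what it changes is data collection. The analysis does not need it either, because mITT is meant to keep violators and PP exists to set them aside. The protocol therefore allows endpoint data to lapse in subjects whom the primary analysis must count.

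The lapse could be related to outcome. Taking a prohibited antiviral, for example, is something a subject who begins to feel unwell might do. The exemption in Protocol 6.2.2 starts only at hospital-level care, whereas the primary endpoint captures much milder illness.

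The ITT run is the planned check on excluding undosed subjects after randomisation. It can serve that purpose only if those subjects have an observed Day 14 outcome.

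**Working it through.** **The plan's own figures.** For 80% v 90%, alpha 0.025 two-sided and 80% power, the unpooled formula gives n = (0.8×0.2 + 0.9×0.1)(2.2414 + 0.8416)²/0.10² = 237.6, so 238, as stated. The plan rounds to 240, and 240/0.90 = 266.7, so 267. Ordinary loss of 10% is thus already budgeted.

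**What lapses.** Take a subject dosed on Day 1 and removed on Day 4.

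- Scheduled contacts after Day 1 up to Day 14 fall on Days 3, 5, 7, 9, 11 and 14. Five of the six come after Day 4.
- The home log runs daily through Day 14 (Protocol 7.2.1). The last 14 − 4 = 10 days are no longer required.
- The Day 14 checklist and oxygen saturation are done on Day 4 and describe the subject up to Day 4.
- Day 29 has a symptom checklist (7.2.8), but the text does not say that it looks back over Days 5 to 14.
- The subject stays in mITT. SAP 4.4 promises worst-case imputation where applicable, with details in Section 6, but SAP 6.1 states no rule for the primary endpoint.

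**Undosed subjects.** The first sentence of 5.3.4 covers dosed subjects only. The second covers all withdrawals except screen failures. A randomised, undosed subject who leaves is outside the first and inside the second.

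**Illustration 1: power.** The loss shares are assumptions. Power = Φ[(Δ√n − 1.96√(2p̄q̄))/√(p₁q₁ + p₂q₂)] at two-sided 0.05. With all 267 per arm: (0.1×16.34 − 1.96×0.505)/0.5 = 1.289, or 90.1%.

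| Lost per arm | Excluded | Counted asymptomatic | Counted symptomatic |
|---|---|---|---|
| 2% | 89.5% | 89.4% | 86.1% |
| 5% | 88.6% | 88.3% | 79.7% |
| 10% | 86.9% | 86.3% | 69.0% |

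At the planning alpha of 0.025, 10% excluded leaves 79.9%, which is the planned figure to rounding. Values below 80% at 0.05 appear only in the last column, under a rule that SAP 6.1 does not state for this endpoint.

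**Illustration 2: bias, extreme case.** Suppose the true rate is 80% in both arms, only the active arm loses subjects, all of them would have become symptomatic, and they are excluded. The observed active rate is 0.8/(1 − m). For m = 2%, 5% and 10% the spurious gain is 1.6, 4.2 and 8.9 points. The chance of a false significant benefit is about 7%, 24% and 79%, against a nominal 2.5% in that direction. This is an upper bound on harm, not a forecast.

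**Illustration 3: ITT.** Suppose u undosed subjects are scored symptomatic, with 267 per arm and a pooled z test at the expected rates.

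- u = 0: difference 10.0 points, z = 3.24, p = 0.001.
- u = 5 in the 2 g arm only: 0.9×262/267 = 88.3%, difference 8.3 points, z = 2.63, p = 0.009.
- u = 10 in the 2 g arm only: 0.9×257/267 = 86.6%, difference 6.6 points, z = 2.05, p = 0.04.
- u = 5 in each arm: p = 0.002. u = 10 in each arm: p = 0.004.

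**The case against.** Several stronger readings are tempting, and the documents do not support them.

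*Removal ends outcome collection.* It does not. Withdrawal is permitted, not required. Data gathered earlier are kept (Protocol 5.3), the checklist is repeated at withdrawal, and Days 29 and 60 are retained, so an observed event stays an event. Many Day 29 outcomes (hospital, ICU, ventilation, oxygen, death, medically attended visits) remain obtainable. The loss is confined to required ascertainment of the primary endpoint, and of time to symptoms, between removal and Day 14.

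*Undosed subjects are not followed and have no Day 14.* Neither is stated. Non-dosing is not itself a ground for withdrawal, and the second sentence of 5.3.4 reaches undosed subjects who leave. SAP 4.3 works by nominal visit, and randomisation takes place on Day 1. What stands is two sentences that need reconciling and a Study Day rule with no dosing date to use.

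*Non-dosing will differ by arm.* Protocol 4.4.1 says of the product "The solution must not be used if the solution is cloudy or turbid", and the dosing nurse is unblinded. But nothing says that the subject then goes undosed. Dosing follows randomisation at the same visit, so the number is probably small. Undosed subjects are outside mITT, so only the ITT sensitivity analysis is touched.

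*The trial is underpowered as a result.* No stated power is shown to be missed, since 10% withdrawal is already allowed for.

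It can also be said that striking two grounds from 5.3.2 changes little while 5.3 lets the investigator withdraw anyone at any time. That is fair, and the fix has to cover that discretion too.

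**Conclusion.** The point holds in a limited form. In a single-dose trial, 5.3.2 and 5.3.4 together let a subject who must be counted in mITT lose required primary-endpoint ascertainment before Day 14, on grounds that serve no analysis purpose and may be related to outcome. Separately, Day 14 follow-up of randomised but undosed subjects is not clearly provided for, which weakens the ITT run as a check on mITT.

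The size is unknown. The documents give neither a removal rate nor an undosed count, so the power, bias and p-value figures above are illustrations under assumed counts. The case for change rests on avoidable, possibly informative missing data and a cheap remedy, not on a demonstrated shortfall.

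**What to change.** - **Protocol 5.3.2:** remove major protocol violations and sponsor request as grounds for ending an individual subject's follow-up. State that violators stay in follow-up and in mITT and are handled through the PP population.
- **Protocol 5.3:** apply the same limit to the investigator's general discretion to withdraw, leaving grounds concerned with the subject's well-being untouched.
- **Protocol 5.3.4:** reconcile the first two sentences so that the section applies to all randomised subjects, dosed or not. Keep the scheduled contacts and the home log through chronological Day 14, then Days 29 and 60, unless consent is withdrawn.
- **SAP 4.6:** for undosed subjects in the ITT analysis, use the nominal Day 14 visit, counted from the Day 1 randomisation visit.

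The cost is wording in both documents and a few contacts that are already in the schedule. The sample size does not change. The missing-data rule absent from SAP 6.1 is a separate matter, but it determines how any remaining gaps are scored and should be settled alongside this.
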